#### 3.2 Risk/Benefit Assessment

The most serious risk associated with retinoids is related to teratogenicity and embryotoxicity. CD5789, like all retinoids, may cause fetal harm following systemic exposure in pregnant women. Therefore, women of childbearing potential will be required to be strictly abstinent or to use an effective contraceptive method during the study and for at least one month after the last study drug application. Postmenopausal status, where relevant, will be assessed and confirmed prior to subject participation in the study.

Topical retinoids may be associated with skin irritation, particularly in the two first weeks of therapy (Leyden 1998). CCI

Long-term safety data for the trifarotene product have shown that the safety profile remains stable with a long-term use. Therefore, given the documented effectiveness of trifarotene cream  $50~\mu\text{g/g}$  in the treatment of acne, the benefit/risk of 6 months' exposure to treatment with trifarotene or vehicle is considered to be positive.

Any subject is free to discontinue his/her participation in this clinical trial at any time and for whatever reason, specified or unspecified, without any prejudice. No constraints are to be imposed on the subject, and when appropriate, a subject may be treated with other conventional therapy when clinically indicated.

No invasive methods will be used during this trial.

Subjects will be followed regularly during the trial, especially for adverse events, approximately once a month for 6 months.

GALDERMA R&D RD.06.SPR.204245 V00 18AUG2021 Page 24 of 104

Consequently, based on available safety data and the proposed trial design, no safety issues others than those reported are expected following topical administration of trifarotene cream.

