- 7. Subject having read, understood and signed the approved Informed Consent Form (ICF) prior to any participation in the clinical trial. Subject under the age of 18 having signed an assent form to participate in the clinical trial and their parent(s) or legal representative having read and signed the informed consent form prior to any clinical trial related procedures, samples and photos are collected,
- 8. Apprised of the Health Insurance Portability and Accountability Act (HIPAA), if in the US and is willing to share personal information and data, as verified by signing a written authorization at the screening visit.
- 9. Subject willing and able to comply with the requirements of the trial protocol. Subject must adhere to the visit schedule, concomitant therapy prohibitions, and must be compliant to the treatment. (for subjects who are minors, the

with trifarotene 50 μg/g	cream ve	ersus vehicle cream over 24 weeks.	
		parent(s)/legal representative must be also willing and able to help comply with study requirements).	p the subject
Exclusion criteria	Sul	bjects meeting any of the exclusion criteria are not eligible to particular.	cipate in the
	1.	Subject with severe acne (IGA > 3),	
	2.	Subject with more than 1 nodule/cyst on the face (excluding the r	nose),
	3.	Subject with acne conglobata, acne fulminans, secondary acne (c induced acne, etc.), nodulocystic acne, acne requiring systemic tr	
	4.	Subject with damaged facial skin (e.g., tattoo, skin abrasion, ecze sunburned skin) that may interfere with study assessments,	ema or
	5.	Female subject who is pregnant, lactating or planning a pregnanc study,	y during the
	6.	Female subject of childbearing potential using combined oral corapproved as acne treatments (e.g., Ortho Tri-Cyclen®, Yaz®, Dia whom the dose has not been stable for at least 6 months prior to tvisit,	ane-35®), in
	7.	Subject with known impaired hepatic or renal functions,	
	8.	Subject with a wash-out period for topical treatment or procedure less than:	es on the face
		Topical treatments: Corticosteroids, antibiotics, benzoyl peroxide, azelaic acid, hydroxyacids, Zinc containing treatments, other anti-inflammatory drugs or other acne treatments (for example salicylic acid treatments/ transdermal contraceptives are forbidden if used to treat acne)	2 Weeks
		Retinoids (including fixed drug combinations)	4 Weeks

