# 5.1.1.2 Study Assessment Schedule

	CLINICAL TRIAL VISITS									
	Visit 1	Visit 2	Visit 3	Visit 4	Visit 5	Visit 6	Visit 7	Visit 8	Visit 9	Visit 10
PROCEDURES	Screening (Up to 28 days prior to Baseline)	Baseline	Week 1 (±1 d)	Week 2 (±1 d)	Week 4 (±3 d)	Week 8 (±3 d)	Week 12 (±3 d)	Week 16 (±3 d)	Week 20 (±3 d)	Week 24 (±5 d) or ET
Informed consent/Photography Consent	X									
Inclusion/Exclusion Criteria	X	X								
Demographics/ Relevant medical history/ Prior therapies a	X									
Urine Pregnancy test (UPT) b	X	X			X	X	X	X	X	X
Efficacy Assessments										
Overall Disease Severity PIH Score assessed by the investigator	X	X					X	X	X	X

GALDERMA R&D RD.06.SPR.204245 V00 18AUG2021 Page 30 of 104

	CLINICAL TRIAL VISITS									
	Visit 1	Visit 2	Visit 3	Visit 4	Visit 5	Visit 6	Visit 7	Visit 8	Visit 9	Visit 10
	Screening (Up to 28 days prior to Baseline)	Baseline	Week 1 (±1 d)	Week 2 (±1 d)	Week 4 (±3 d)	Week 8 (±3 d)	Week 12 (±3 d)	Week 16 (±3 d)	Week 20 (±3 d)	Week 24 (±5 d) or ET
Safety Assessments										
Local tolerability assessment of face		X	X	X	X	X	X	X	X	X
Adverse events c	X	X	X	X	X	X	X	X	X	X
Concomitant therapies	X	X	X	X	X	X	X	X	X	X
	Investigational Product Administration									
Dispensation of investigational products and subject diary		X			X	X	X	X	X	
Dispensation of non-investigational products		X			X	X	X	X	X	

GALDERMA R&D RD.06.SPR.204245 V00 18AUG2021 Page 31 of 104

	CLINICAL TRIAL VISITS									
	Visit 1	Visit 2	Visit 3	Visit 4	Visit 5	Visit 6	Visit 7	Visit 8	Visit 9	Visit 10
PROCEDURES	Screening (Up to 28 days prior to Baseline)	Baseline	Week 1 (±1 d)	Week 2 (±1 d)	Week 4 (±3 d)	Week 8 (±3 d)	Week 12 (±3 d)	Week 16 (±3 d)	Week 20 (±3 d)	Week 24 (±5 d) or ET
Return of investigational products and accountability					X	X	X	X	X	X
Subject Diary/Compliance d			X	X	X	X	X	X	X	X
Exit form										X

- a. Only prior therapies that were stopped within 6 months of the Baseline visit and that may have an impact on inclusion/exclusion criteria should be recorded. Treatment that continues after Baseline should be recorded on the Concomitant Treatment Form of the CRF.
- b. For Subject of childbearing potential: UPT should be conducted if no menstrual period in the preceding four weeks. Urine Pregnancy Tests are mandatory at Baseline and at Week 24 / ET (early termination).
- c. Adverse event onsets after subject signature of the informed consent form should be recorded on the AE Form of the CRF.

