- d. Subject diary is a diary which will be given to the subject to report the treatment application.
- e. Comedones (open and closed), Papules, pustules, nodules will be counted.
- f. For assessments where 3 target lesions are mentioned, the same 3 target lesions on the subject's face should be used throughout the study.
- g. To be performed between Week 24 and Week 26 by Evidera (CRO), if consented.

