#### 5.3.2 Inclusion Criteria

Subjects must fulfill inclusion criteria to participate in the study:

- 1. Male or female subject of any ethnic background of at least 13-35 years old,
- 2. Subject with clinical diagnosis of acne vulgaris, defined by:
  - a) moderate acne on the face (IGA=3);
  - b) with minimum of 20 inflammatory lesions and 25 non inflammatory lesions on the face (excluding the nose);
  - c) moderate to marked PIH on the face (ODS hyperpigmentation scale 4-6);
  - d) No more than one acne nodule or cyst (> 1 cm) on the face (excluding the nose),
- 3. Subject with any Fitzpatrick Skin Type I to VI (target patient enrollment according to FST),
- 4. Female subjects of childbearing potential must have a negative urine pregnancy test (UPT) at Baseline visit (Visit 2),
- 5. Female subjects of childbearing potential (ie, fertile, following menarche and until becoming post-menopausal unless permanently sterile) must agree either to commit to true abstinence throughout the study, when this is in line with the preferred and usual lifestyle of the subject, or to use an adequate and approved method of contraception throughout the study. This criterion also applies to a prepubertal female subject who begins menses during the study.

\*In Germany only, if a subject has reached Tanner stage 3 breast development, even if not having menarche, the subject will be considered a female of childbearing potential. Periodic abstinence (e.g. calendar, ovulation, symptothermal, post-ovulation methods) and withdrawal are not acceptable methods of contraception.

Adequate and approved methods of contraception applicable for the subject and/or her partner are defined below:

- Progestogen-only oral hormonal contraception
- Combination of male condom with cap, diaphragm, or sponge with spermicide (double barrier methods) (\*In Germany only, double barrier methods are not considered an adequate and approved method of contraception).

Note: "double barrier methods" refers to simultaneous use of a physical barrier by each partner. Use of a single barrier method (e.g. condom) together with a spermicide is not acceptable.

- Combined (estrogen- and progestogen-containing) oral, intravaginal, or transdermal hormonal contraception
- Injectable or implanted hormonal contraception
- Intrauterine devices or intrauterine hormone-releasing system
- Bilateral tubal ligation or tube insert (such as the Essure system) at least 3 months before the study

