- Bilateral vasectomy of partner at least 3 months before the study
- 6. Female of non-childbearing potential, e.g.: premenses, post-menopausal (absence of menstrual bleeding for 1 year prior to Baseline, without any other medical reason), hysterectomy, bilateral salpingectomy, bilateral oophorectomy,
- 7. Subject having read, understood and signed the approved Informed Consent Form (ICF) prior to any participation in the clinical trial. Subject under the age of 18 having signed an assent form to participate in the clinical trial and their parent(s) or legal representative having read and signed the informed consent form prior to any clinical trial related procedure, samples and photos are collected,
- 8. Apprised of the Health Insurance Portability and Accountability Act (HIPAA), if in the US and is willing to share personal information and data, as verified by signing a written authorization at the screening visit.
- 9. Subject willing and able to comply with the requirements of the trial protocol. Subjects must adhere to the visit schedule, concomitant therapy prohibitions, and must be compliant to the treatment. (for subjects who are minors, the parent(s)/legal representative must be also willing and able to help the subject comply with study requirements).

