#### **5.3.3** Exclusion Criteria

Subjects meeting any of the exclusion criteria are not eligible to participate in the study:

- 1. Subject with severe acne (IGA > 3),
- 2. Subject with more than 1 nodule/cyst on the face (excluding the nose),
- 3. Subject with acne conglobata, acne fulminans, secondary acne (chloracne, drug-induced acne, etc.), nodulocystic acne, acne requiring systemic treatment,
- 4. Subject with damaged facial skin (e.g. tattoo, skin abrasion, eczema or sunburned skin) that may interfere with study assessments,
- 5. Female subject who is pregnant, lactating or planning a pregnancy during the study,
- 6. Female subject of childbearing potential using combined oral contraceptives approved as acne treatments (e.g., Ortho Tri-Cyclen®, Yaz®, Diane-35®), in whom the dose has not been stable for at least 6 months prior to the Baseline visit,
- 7. Subject with known impaired hepatic or renal functions,
- 8. Subjects with a washout period for topical treatment or procedures on the face less than:

Topical treatments: Corticosteroids, antibiotics, benzoyl peroxide, azelaic acid, hydroxyacids, Zinc containing treatments, other anti-inflammatory drugs or other acne treatments (for example salicylic acid treatments/ transdermal contraceptives are forbidden if used to treat acne)	2 Weeks
Retinoids (including fixed drug combinations)	4 Weeks
Cosmetic/aesthetic procedures on the face (e.g., comedone extraction, desquamating, or abrasive agents, adhesive cleansing strips)	1 Week
Wax epilation	2 Weeks
Photodynamic therapy	6 Weeks
Laser therapy, microdermabrasion, deep chemical peel, plastic surgery for acne	3 months

9. Subject with a washout period for systemic treatment less than:

Corticosteroids, (except locally acting corticosteroids such as inhaled or intrathecal or dermal application at distance from the face), tetracyclines, other antibiotics (except penicillin)	1 month
Oral retinoids/isotretinoin	6 months

Cyproterone acetate / Chlormadinone acetate						
Spironolactone/ Drospirenone	3 months					
Immunomodulators	3 months					
Oral contraceptives for acne	1 month					

Note: No time frame period is specified for medicated shaving creams, after-shaves, colognes, astringents, or preparations with alcohol, but their application is prohibited during the study.

- 10. Subject with active or chronic skin allergies,
- 11. Subject with known or suspected allergy to the investigational product,

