# 5.5 Duration of Subject Participation

The expected duration for each subject's participation in the study is approximately 7 months (24 weeks (6 months) of treatment and up to 28-day period between screening and baseline).

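### Inclusion 5 and exclusion 5 stop at the end of the study, although Protocol 3.2 requires contraception for at least one further month after the last application

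*Protocol*

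**What the plan says.** Protocol 3.2 names teratogenicity and embryotoxicity as the most serious retinoid risk. It then states a requirement for women of childbearing potential: strict abstinence, or "to use an effective contraceptive method during the study and for at least one month after the last study drug application".

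Inclusion criterion 5 (synopsis and 5.3.2) is the criterion that puts contraception into practice. A woman must agree to true abstinence for the length of the study, "or to use an adequate and approved method of contraception throughout the study".

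Exclusion criterion 5 (5.3.3, with the same criterion in the synopsis) rules out a "Female subject who is pregnant, lactating or planning a pregnancy during the study".

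Inclusion criterion 9 is general: "Subject willing and able to comply with the requirements of the trial protocol".

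Section 5.5 puts participation at approximately 7 months, made up of "24 weeks (6 months) of treatment and up to 28-day period between screening and baseline". The schedule in 5.1.1.2 places the last clinic visit and the last mandatory pregnancy test at Week 24 or early termination.

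**The concern.** Section 3.2 sets two periods, the study and the month after it. The two criteria that name contraception and planned pregnancy mention only the first. A woman who intends to conceive two weeks after her last application would meet inclusion 5 and exclusion 5 as worded, yet would not meet the rule in 3.2.

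Sites screen against the numbered criteria, so one working from them could give the shorter instruction. Several permitted methods (oral contraceptives, double barrier where allowed, abstinence) can stop on the day of the last visit, so the wording can affect what a subject does. The issue is whether a control that the sponsor calls required reaches the criteria meant to apply it. No statistical property of the trial depends on it.

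**Working it through.** **1. Stated duration.** 24 weeks × 7 = 168 days of treatment, and 168 + 28 = 196 days in all. That is 196 / 30.4375 = 6.4 calendar months, or 7 if 24 weeks are counted as 6 months and screening as one more, as 5.5 does. The stated figure is reproduced, and it contains no post-treatment days.

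**2. The texts side by side.**

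| Place | Subject matter | Period covered |
|---|---|---|
| 3.2 | Abstinence or contraception | Study, plus at least one month after last application |
| Inclusion 5 (synopsis, 5.3.2) | Abstinence or contraception | Study only |
| Exclusion 5 (synopsis, 5.3.3) | Planned pregnancy | Study only |
| Inclusion 9 | Compliance with the protocol in general | No period given |

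The study period cannot be read to include the month. Section 3.2 lists the month in addition to the study, and 5.5 ends participation with treatment. Section 11 dates the end of the study as a whole to the last subject's last visit. Using that date would still leave the last women to finish uncovered, and would give each woman an end date that nobody could tell her at enrolment.

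**3. Days of the month outside the criteria, for a woman who doses to Week 24.**

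Inputs:
- Week 24 target day: 169 (SAP 4.2.6).
- Visit window: ±5 days (Protocol 5.1.1.2), so visit day *v* runs from 164 to 174.
- Last application day *L*: either the evening before the visit (*v* − 1), or no later than day 168, when 24 weeks of daily dosing from day 1 end.
- One month *m*: 28 to 31 days (assumption; 3.2 does not define it in days).

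Time from last application to visit, *v* − *L*:
- shortest: 1 day
- longest: 174 − 168 = 6 days

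Uncovered days = *L* + *m* − *v* = *m* − (*v* − *L*):
- smallest: 28 − 6 = 22 days
- largest: 31 − 1 = 30 days
- visit on target day 169 with *L* = 168: the month ends on day 196 to 199, leaving 27 to 30 days

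A woman who stops the drug at least a month before her last visit has no gap. One who leaves at an early termination visit soon after her last application has nearly the whole month uncovered.

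**4. What those days mean pharmacologically.** The label in Protocol Appendix 14.9 gives a terminal half-life of 2 to 9 hours. Five half-lives are 5 × 2 = 10 hours to 5 × 9 = 45 hours, and 45 / 24 = 1.9 days at most. The 22 to 30 days count missing wording. They are not days of equal exposure.

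**The case against.** The strongest reply is that the month is already in the protocol. Section 3.2 states it as a requirement and inclusion 9 demands willingness to follow protocol requirements, so a woman who will not observe it is ineligible on a full reading. That is right as far as it goes. But it leaves the specific criterion silent and relies on a site connecting a general clause to a paragraph in the background section.

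The second reply is that almost nothing is at stake. In the label's pharmacokinetic study, with application to the face, shoulders, chest and upper back, drug was quantifiable in 7 of 19 adults and Cmax reached at most 10 pg/mL. This trial treats the face only. The label lists no contraindications, reports no drug-associated risk identified in trial data, and places animal fetal effects at more than 800 times human exposure. This stands, and it is why the point is minor.

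Third, the documents do not say which text is the error. Deleting the month from 3.2 would also remove the conflict. That is true; extending the criteria is the more cautious choice.

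Three stronger readings are tempting and are not supported:

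- *Women will be told they may stop contraception at Week 24.* The consent form was not available and may state the month. If it does, the mismatch inside the protocol remains, but the subjects are properly informed.
- *Pregnancies in that month would be lost.* Section 5.3.4.1 has any pregnancy found after inclusion followed to term, and provides for an SAE report if the subject has completed the study. No new reporting sentence is needed in 6.3.6.2.5.
- *The lack of scheduled contact after Week 24 is itself a defect.* A schedule footnote mentions an activity by Week 26, but the row it belongs to is not visible. The wording correction needs no extra contact in any case.

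**Conclusion.** The inconsistency is real. Section 3.2 imposes a month that inclusion 5 and exclusion 5 leave out, and 5.5 does not allow the study period to be stretched over it. For a woman dosing to Week 24, the criteria miss about 22 to 30 days. This takes a month as 28 to 31 days and the last application as 1 to 6 days before the visit.

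The severity is low. Absolute risk is probably small given the half-life and systemic levels, and retinoid exposure concerns only the trifarotene arm. No number of affected women can be given: the documents state neither how many will be of childbearing potential nor which methods they will use, and some methods (intrauterine device, implant, tubal ligation, partner vasectomy) carry on without any action. Sample size, error rate and the primary analysis are untouched.

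**What to change.** 1. Inclusion criterion 5, in the synopsis and in 5.3.2: extend the period for both abstinence and contraception so that it runs through the study and until at least one month after the final application of study drug, matching 3.2.
2. Exclusion criterion 5, in the synopsis and in 5.3.3: extend the bar on planned pregnancy to the study period and the month after the final application.
3. Check the consent form and add the month if it is not already there.

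If the sponsor judges the month unnecessary, the alternative is to remove it from 3.2 with a stated reason. Either way the texts should agree.

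The cost is two criteria reworded in two places each, plus matching consent wording if needed. No visit, test, procedure or subject is added.

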### 3.3 Drug Profile

Retinoids play a central part in the treatment of acne due to their keratolytic activity and modulation of proliferation and differentiation of keratinocytes leading to the elimination of comedones (Pawin 2004).

Retinoids exert their effects on a molecular level through nuclear receptors: Retinoic Acid Receptor (RAR) and Retinoic X Receptor (RXR), which each have three sub-types  $\alpha$ ,  $\beta$  and  $\gamma$ .

#### 3.4 Dose Selection Rationale

Trifarotene cream  $50\mu g/g$  when applied once daily for 12 weeks has been shown to be safe and effective in the treatment of acne vulgaris, with FDA-approval for US commercial use granted in October 2019 (Appendix 14.8 - AKLIEF Prescribing Information).

The commercially-approved trifarotene dosing regimen will be used to evaluate efficacy and safety of trifarotene 50  $\mu$ g/g cream versus vehicle cream on the risk of formation of acne-induced post-inflammatory hyperpigmentation.

#### 4 STUDY OBJECTIVE AND ENDPOINTS

#### 4.1 Study Objective

The objective of this study is to evaluate the efficacy and safety of trifarotene 50  $\mu$ g/g cream compared to its vehicle cream in the treatment of moderate acne vulgaris with acne-induced post-inflammatory hyperpigmentation (PIH) in subjects with Fitzpatrick Skin Types (FST) I-VI.

#### 4.2 Study Endpoints

Study endpoints that will support safety and efficacy results are summarized below.

## 4.2.1 Primary Efficacy Endpoint

[figure not shown]
Absolute change from Baseline in PIH Overall Disease Severity scores at Week 24

GALDERMA R&D RD.06.SPR.204245 V00 18AUG2021 Page 25 of 104

# 4.2.2 Secondary Efficacy Endpoints

Post-inflammatory Hyperpigmentation:

- Percent change from Baseline in PIH Overall Disease Severity scores at Week 24
- Absolute and percent change from Baseline in PIH Overall Disease Severity scores at Week 12, 16 and 20.

GALDERMA R&D RD.06.SPR.204245 V00 18AUG2021 Page 26 of 104

### **4.2.4** Safety

- Incidence of Adverse Events
- Local tolerability (erythema, scaling, dryness and stinging/burning)

#### 5 INVESTIGATIONAL PLAN

### 5.1 Overall Study Design

[figure not shown]
This is a multi-center, randomized (1:1), double-blind, vehicle-controlled, parallel-group study evaluating trifarotene cream in treating acne-induced hyperpigmentation in patients with acne. Approximately 120 randomized subjects aged 13-35 are planned, at approximately 20 study centers in the United States and Europe. Target enrollment should include an approximate distribution of Fitzpatrick Skin Types, 30% light skin (I-III) and 70% dark skin (IV-VI).

Subject eligibility will be evaluated over a 28-day screening period. Qualifying subjects will complete Baseline assessments and be randomized (1:1) to Trifarotene or Vehicle for a 24-week treatment period. Subjects will be provided skin care products including Cetaphil® Gentle Skin Cleanser for washing the face twice daily (morning and evening); Cetaphil® Dermacontrol Moisturizer with SPF 30 for use daily on the face (morning) and to be re-applied to face before sun exposure, and Cetaphil® Moisturizing Lotion for extra moisturizer as needed. If a subject experiences persistent dryness or irritation, the investigator may consider a reduced application frequency for the topical study drug, over a maximum of 2 weeks, within the first four (4) weeks of the treatment period (Section 5.4.8 – Dose Modification of Topical Study Drug).

Subjects who do not require a washout period may complete the Screening and Baseline assessments on the same day. Subjects who initially fail screening may be re-screened once, provided the reason for screen failure is not due to acne severity (IGA) or lesion counts.

Subjects will return to the clinic for safety and efficacy assessment at Weeks 1, 2, 4, 8, 12, 16, 20 and 24. Study procedures and assessments are performed according to the schedule of assessments (Section 5.1.1).

